To fill this critical knowledge gap, we propose a randomized, controlled 12-week trial using incentives to reduce COC use, with an additional 24 weeks of follow up. Over 5 years, subjects will be randomly assigned to one of three groups (n=66 completers/group): 1) high value incentives for COC abstinence in which frequency of COC use is expected to be substantially reduced or eliminated, 2) low value incentives for COC abstinence in which frequency of COC use is expected to be reduced or 3) a non-contingent control group, in which frequency of COC use is expected to remain stable. Three specific aims are proposed:

First, this study seeks to demonstrate that reduced COC use improves physiological and biochemical indicators (i.e., biomarkers) of cardiovascular function. Improvements in cardiovascular function will be assessed with physiological measures of cardiovascular fitness (e.g., peripheral arterial tonomotry) and biomarkers of endothelial (e.g., endothelin-1) and platelet (e.g., soluble CD40L) function.

Second, this study seeks to demonstrate that reduced COC use improves physiological indicators and biomarkers of immune function. Improvements will be assessed with a physiological measure (i.e., delayed-type hypersensitivity) and biomarkers of immune function (e.g., tumor necrosis factor- α , microbiome indicators).

Third, this study seeks to demonstrate that reduced COC use improves psychosocial function. Psychosocial improvements will be assessed with standardized observer and self-reported measures of mental health, drug use and risky behavior, as well as validated and sensitive cognitive behavioral tasks.

Our overarching hypothesis is that individuals assigned to the active treatment conditions (i.e., those who reduce their COC use) will display health improvements compared to individuals assigned to the noncontingent control group both during and after treatment. A "dose-response" is expected whereby individuals assigned to the high value condition will display greater reductions in COC use, and consequently greater improvements, relative to the low value group. We further hypothesize that 1) individuals assigned to active treatment conditions will display improvements from baseline through treatment completion and into follow up and 2) biomarker improvements will predict physiological outcomes.

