4. STUDY POPULATION

Up to 500 individuals will be screened to participate in this protocol. We intend to enroll 300 (150 men, 150 women) subjects, with 198 completers. These individuals must be English-speaking, English-reading subjects 18 years and older of diverse racial and ethnic background. Enrollment in this protocol will occur between September 1, 2017 and August 31, 2022. Subjects will be required to provide legal proof of age.

Inclusion Criteria:

-Age 18 to 65

-Self-report of recent cocaine use verified by a cocaine-positive urine sample

-Meet moderate-severe Cocaine Use Disorder Criteria

-Seeking treatment for their cocaine use

-Able to commit to 12-week intervention, plus 24-week follow up

-Participants who have taken antibiotics within 30 days of sample collection will be excluded from the microbiome assay.

Exclusion Criteria:

-History of serious physical or psychiatric disease (e.g., physical dependence on any drug requiring medically managed detoxification, unstable angina, uncontrolled cardiac arrhythmia, aortic stenosis, self-reported compromised immune function, extreme hypersensitivity/allergy to candida yeast or similar products, severe diagnosis for other substance use disorder) that would interfere with study participation

-Current physical or psychiatric disease that would interfere with study participation

-Poor venous access, precluding blood draws

During the initial screening interview and prior to sessions, potential subjects will be asked to provide a urine specimen that will be screened for the presence of a range of drugs including amphetamine, benzodiazepines, barbiturates, cocaine, tetrahydrocannabinol (THC) and opioids. Temperature will be recorded and the presence of adulterants will be tested using measures of creatinine, nitrite, pH, bleach, and specific gravity. Temperature and adulterant tests are included in the CLIAwaived brand rapid drug test cup. Evidence of urine sample adulteration will result in subject dismissal from the study.

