7. RESEARCH PROCEDURES

Subjects who are deemed potentially eligible after an initial telephone screen and express interest in participation will be scheduled for an in-person, intake interview. After providing informed consent, subjects will self-report medical, psychiatric, drug use and substance use disorder treatment histories. They will also be asked for contact information for themselves (e.g., postal address, phone, text message, email, social media) and two other individuals who know how to reach the subject. This information will be collected as a way to minimize loss of contact with subjects and prevent missing data. To further prevent missing data, subjects will be offered transportation to/from the laboratory for study visits. We are using similar methods in our ongoing clinical trial, as noted above, resulting in very little missing data.

Preliminary health assessments will include vital signs, weight and height measurement, urine drug screening, standard laboratory chemistries (i.e., hemogram with differential, c reactive protein, chemistry panel 23, lipid panel, troponin, uric acid, cortisol) and an electrocardiogram (ECG). Psychological assessments will include a DSM-5 diagnostic interview (SCID-5) and the Addiction Severity Index-Lite (ASI), conducted by trained and qualified interviewers. The ASI will complement the SCID-5 by providing data on physical and mental health, alcohol and drug use, employment, legal status and family/social support. Study investigators will review these materials for inclusion/exclusion criteria and if a subject is deemed eligible and accepts the offer to participate, he/she will complete additional baseline measures (e.g., peripheral arterial tonometry) and be urn-randomized to one of three study groups. Any abnormalities detected at screening that result in exclusion from participation will be disclosed to subjects, who will be encouraged to follow up with their physician or the public health department. Should abnormalities be detected after randomization into the study, our study physician, [name], will determine the best course of action. [name] will consult with [name] should abnormalities be related to cardiovascular outcomes.

Random Assignment

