urine sample outcome. Subjects will earn \$60 for each Post Intervention visit. Subjects will also earn \$15 for completing a follow up visit to have their DTH response measured 48 hours after their 4, 12 and 24 Week Post visit. To increase completion rates, subjects will receive half of the visit payment (e.g., \$30 for the 6 Week visit) at the end of each study visit. The remaining half will be paid upon study completion. If a subject completes all study visits, he or she can earn approximately \$1,230 in study payments.

Data Analysis

The statistical significance criterion is $p \le 0.05$.

Aim 1: To demonstrate that reduced COC use improves physiological and biochemical indicators (i.e., biomarkers) of cardiovascular function. Time-and group-varying weekly number of BE-negative urine samples will be analyzed as the primary predictor of cardiovascular outcomes (e.g., endothelin-1 levels) using generalized linear mixed models (GLMM; Stata 14, College Station, TX). All models will be constructed using intent-to-treat analyses including non-completing subjects, whereby the group to which the participant is randomized will be utilized. GLMM are particularly well suited for analyses of longitudinal data, as they allow for multiple observations over time, correlations among observations within an individual subject, for subjects measured at different time points and for baseline covariates (e.g., sex; age; race) and covariates that change over time (e.g., alcohol use). Although GLMM allow for missing data, any missing data will first be tested to determine whether they are missing at random or missing not at random (MNAR). Any data MNAR will be subject to multiple imputation.

Aim 2: To demonstrate that reduced COC use improves physiological indicators and biomarkers of immune function. Time- and group-varying weekly number of BE-negative urine samples will be analyzed as the primary predictor of immune outcomes (e.g., IL-10 levels) using GLMM. Other details are the same as for cardiovascular outcomes.

Aim 3: To demonstrate that reduced COC use improves psychosocial function. Time-and groupvarying weekly number of BE-negative urine samples will be analyzed as the primary predictor of psychosocial outcomes (e.g., other drug use) using GLMM. Other details are the same as for cardiovascular outcomes.

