The primary outcome measure in this study will be the influence of reduced cocaine use on endothelin-1 levels. Secondary outcome measures include other cardiovascular, immune and psychosocial function. Data will be analyzed as described in the research plan. The alpha level will be set at 5%.

As noted above, wherever possible, data are collected using an automated computer system, which increases the accuracy and completeness of data collection and ensures the validity and integrity of the data. The quality of data analyses will be monitored by random inspection by the PI and/or Co-Investigators.

Safety Monitoring Plan. Potential subjects will provide information regarding their drug use history and undergo an extensive physical and psychiatric health screening to determine their eligibility and safety of their participation. Potential subjects must meet DSM-5 criteria for moderate-severe cocaine use disorder and must present with a urine sample positive for cocaine/benzoylecgonine at the time of screening. Any potential subject with poor venous access, self-disclosed compromised immune function or who has experienced an allergic reaction to candida yeast or similar products will be excluded. Methods for monitoring adverse events (AEs) will include observations by the medical and research staff, spontaneous report by the subjects and regular measures of physiological function.

All AEs occurring during the course of each study will be collected, documented and reported to the PI and physician co-investigators. The occurrence of AEs will be assessed for the duration of participation and during the follow up visits at 2 and 4 weeks following study completion. Each week a study investigator will review the AE forms from the previous week for events that were reported as new or continuing. The study investigators will follow all AEs to the point of a satisfactory resolution. Subjects may be withdrawn from the study if the medically responsible investigator (i.e., [name], in consultation with [name] if applicable) determines it is the best decision in order to protect the safety of the subject. All AEs will be assessed to determine if they meet criteria for a serious adverse event (SAE).

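### The missing-data rule rests on a MAR-versus-MNAR test that observed data cannot decide, sends 'MNAR' data to multiple imputation with no MNAR model, and has no sensitivity analysis behind it

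*Combined protocol and SAP*

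**What the plan says.** Section 7, Data Analysis, Aim 1 plans generalized linear mixed models (GLMM) with the weekly number of BE-negative urine samples as the main predictor. On the analysis set it says "All models will be constructed using intent-to-treat analyses including non-completing subjects", so incomplete records enter the main models. On missing data it says "any missing data will first be tested to determine whether they are missing at random or missing not at random (MNAR", followed by "Any data MNAR will be subject to multiple imputation". Aims 2 and 3 each add "Other details are the same as for cardiovascular outcomes", which carries the rule to the immune and psychosocial outcomes.

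Other relevant statements:

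- Section 17: "The primary outcome measure in this study will be the influence of reduced cocaine use on endothelin-1 levels".
- Section 1, the overarching hypothesis: subjects in the active arms "will display health improvements compared to individuals assigned to the noncontingent control group both during and after treatment".
- Section 4: "We intend to enroll 300 (150 men, 150 women) subjects, with 198 completers". The word completer is not defined.
- Section 7, on preventing missing data: "We are using similar methods in our ongoing clinical trial, as noted above, resulting in very little missing data".
- Table 1: biomarkers are measured at baseline, Weeks 6 and 12, and 4, 12 and 24 weeks after the intervention.

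**The concern.** The rule lets an unnamed test choose the analysis after the data have been seen, and the question put to that test has no answer in the data. Where the label MNAR is applied, the remedy is an imputation with no stated model. Standard imputation makes the very assumption that the label rejects.

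What is at stake is the reader's ability to judge the endothelin-1 result and the arm comparisons when a sizeable share of subjects may be incomplete. Section 7 leaves positive samples unpaid in both incentive arms but pays the control arm for any sample, so attendance could be related to cocaine use differently by arm. Use recorded before dropout can be conditioned on. Use and endothelin-1 at a missed visit cannot, so MNAR cannot be excluded.

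**Working it through.** The plan states no figure to reproduce here. The check has four steps.

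**1. Can the test be done?** Let Y be the outcome, X the observed history and R = 1 if Y is observed. MAR requires f(Y | X, R=0) = f(Y | X, R=1). The data identify f(Y | X, R=1) and P(R | X), but carry no information on f(Y | X, R=0). They can count against missingness completely at random, but cannot separate MAR from MNAR without untestable assumptions.

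A simulation shows this (2,000,000 subjects, 34% missing, missingness depending on a baseline covariate). Unseen values were shifted by 0, 0.25 or 0.5 SD. The observed mean (-0.066) and observed slope (0.500) were the same in all three cases. The true means were 0.00, 0.085 and 0.170.

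**2. Does the remedy help?** In the same example, standard MAR imputation gave a mean of about 0.00 each time. The size of the bias is missing share × shift: 0.34 × 0.25 = 0.085 SD and 0.34 × 0.5 = 0.17 SD. At 10% missing with a 0.5 SD shift it is 0.10 × 0.5 = 0.05 SD. In the trial-like simulation of step 4 (outcome-driven dropout in the incentive arms, 34% lost), the bias in the high-versus-control contrast was -0.144 SD with MAR imputation and -0.141 SD with likelihood. Imputation can be run under MNAR, but only with a stated MNAR model, and none is given.

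**3. Is there a sensitivity analysis elsewhere?** The Other Analyses paragraph in section 7 varies the cocaine-use indicator, correlates biomarkers with physiology, compares with norms and groups subjects by percentage negative. None of these varies the missing-data assumption. The contact, transport and payment provisions concern prevention.

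**4. How large could the effect be?** From section 4: 300 - 198 = 102, and 102/300 = 34%. This is planned non-completion, not a stated fraction of missing endothelin-1. All of the following are assumptions:

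- Three arms of 100, with weekly negatives out of three averaging proportions of 0.20, 0.35 and 0.55 (control, low, high).
- Outcome SD 1 and within-subject correlation 0.5.
- Endothelin-1 at Weeks 6 and 12, the visits at which a thrice-weekly urine count exists.
- Monotone dropout at log-odds 1 per SD.
- Baseline-adjusted random-intercept likelihood, or generalised least squares with the assumed correlation.

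The slope is in outcome SD per SD of weekly negative count. Ranges cover repeat simulations.

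| Dropout depends on | Lost by Week 12 | True slope | Slope bias | High-versus-control bias (SD) |
|---|---|---|---|---|
| Unseen outcome, incentive arms only | 34% | 0 | -0.016 to -0.018 | -0.13 to -0.14 |
| Unseen outcome, incentive arms only | 34% | -0.28 | -0.004 | -0.156 |
| Unseen outcome, incentive arms only | 16% | 0 | -0.007 to -0.010 | about -0.06 |
| Unseen outcome, all arms alike | 34% | -0.28 | +0.020 | -0.01 |
| Current unseen use only | 34% | 0 | 0.001 or less in size | 0.002 or less in size |
| Current unseen use only | 34% | -0.28 | 0.001 or less in size | -0.025 to -0.06 |

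The 16% case approximates 34% being reached only at the fifth post-baseline biomarker visit. With equal proportional loss per visit, 1 - 0.66^(2/5) = 0.15 are lost by Week 12. Reversing the sign of the log-odds reverses the bias (34% lost, true slope 0: slope +0.019, contrast +0.140). With arm terms in the model, the slope bias in the first row falls to about 0.00.

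**The case against.** The strongest reply is that the defect hardly touches the planned analysis. The primary model regresses the outcome on use, and a regression conditional on use is not biased by dropout that depends only on use. The payment rule suggests that kind of dropout, not dropout driven by unseen endothelin-1. Either branch of the rule also yields an analysis, and by default both rest on MAR, which is a reasonable primary assumption. The Data Analysis section specifies no high-versus-control contrast for endothelin-1. All of this stands, and it limits the size of the point.

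A reader might infer more: that false-positive rates would rise to 10% or even 25%, or that the primary result would be invalid. The documents do not support that. In simulation, rates of about 20% to 25% for the arm contrast arose only at log-odds 1, with dropout driven by the unseen outcome in the incentive arms alone and all 34% lost by Week 12. With 16% lost by then the rate was about 9%, and with dropout on current use it was about 5%. No section describes outcome-driven dropout or says when non-completion occurs.

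The expectation of very little missing data is not a full answer. It describes another trial, it sits beside a planned 34% non-completion, and the test would remain undecidable however little was missing. Nor are the arm contrasts peripheral: section 1 hypothesises them, and the Sample Size Justification speaks of comparing the three groups.

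**Conclusion.** The rule is wrong as written for all three aims. This part rests on logic and on the text, not on any assumed dropout model, and confidence in it is high. Without a sensitivity analysis, the trial could not show that its results are robust to departures from MAR, even if they are.

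The sizes are illustrative. For the planned slope, a bias of 0.02 SD or less is likely (0.020 is about 7% of an assumed slope of 0.28), and about zero if dropout depends only on use. For the arm contrasts with no true effect, outcome-dependent dropout in the incentive arms only gives about 0.06 SD with 16% lost by Week 12 and up to about 0.14 SD with 34% lost. The direction is unknown. The point should be fixed, but it does not show that the primary analysis is seriously biased.

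**What to change.** 1. Delete the test of MAR against MNAR and the sentence that depends on it.
2. State MAR as the primary assumption for the GLMM on all randomised subjects, for all three aims.
3. If multiple imputation is used, run it under MAR with auxiliaries already collected: adjacent urine results, Timeline Follow Back and attendance. Specify the imputation model in advance.
4. Prespecify a delta-adjusted (pattern-mixture) tipping-point analysis, with shifts allowed to differ by arm, for the outcome-on-use slope and for any arm contrast that will be reported. Report the shift at which each conclusion changes.

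For scale, in the assumed two-visit model a 0.5 SD shift of imputed values in both incentive arms moves the slope by 0.017 and the high-versus-control contrast by 0.14 SD. Over all five biomarker visits the figures are 0.009 and 0.11 SD.

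The sensitivity analysis shows dependence on the assumption; it does not correct bias. The cost is a few sentences in the analysis plan and modest extra programming, with no new data or visits.

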After screening, consenting subjects deemed eligible will be enrolled in a 12-week intervention, with a 24week post intervention follow up period. Subjects will be urn-randomized to one of three groups: 1) high value incentives, 2) low value incentives or 3) non-contingent control. An urn randomization process will be used to assign subjects to the three conditions. This method is designed to balance groups on important biological variables that may independently influence outcome. Subjects will be randomized based on sex (male/female), age (>35/≤35 years) and COC use (>15/≤15 days used in the past 30). These characteristics will be determined based on responses to the ASI completed during screening. [name] will perform the randomization and notify non-blind study staff of group assignment. Subjects will be assigned 1:1:1 to the high value, low value and non-contingent control groups.

Alternative Reinforcers for Reduced COC Use: Schedules of Reinforcement and Procedures

Subjects will be assigned to one of two schedules of reinforcement (high and low value incentives) for providing BE-negative urine samples or to a non-contingent control group who will receive money for simply providing a urine sample at each visit.

Subjects assigned to the high value condition will receive \$55 for providing a BE-negative urine sample. Subjects assigned to the low value condition will receive \$13 for providing a BE-negative urine sample. Providing a BE-positive urine sample will result in no payment for that sample in either the high or low value group. Subjects assigned to the control condition will receive \$13 per urine sample they provide independent of test results. Subjects will also be paid for attending study visits during the protocol (see below), independent of urine result outcome, to increase attendance and minimize missing data.

The nature of the intervention prevents subjects from being blind to their assigned condition (i.e., subjects need to be told whether they will earn money for BE-negative urine samples or will earn money for simply providing a urine sample), but subjects will be instructed not to discuss the details of their participation with other subjects or study staff. To enhance rigor and reduce bias, study staff who complete post-randomization assessments, as well as the biostatistician, will be blind to the assigned condition for each subject.

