Defining Reduction in Frequency of COC Use. Subjects will provide observed urine samples thrice weekly (i.e., Monday, Wednesday and Friday) during the 12-week intervention. This thrice weekly urine collection schedule was selected based on the detection time of BE in urine (i.e., up to 72 hours after use; 89) and because the study on which our incentive schedule is based used thrice weekly testing. All urine samples will be coded as positive or negative using qualitative urine BE screens that have a 300 ng/ml cutoff, a criterion used in many recent clinical trials and the criterion used by Higgins and colleagues (Higgins et al., 2007). Using this approach will allow estimates of the levels of reduction observed in each of the three groups (see above).

The number of BE-negative urine samples provided across each week of the trial, out of a maximum of three each week, will be calculated for each subject to determine how group assignment impacted frequency of use. *Experts recently recommended that frequency of use, rather than quantity of use, be the target for reduction (Kiluk et al., 2016).* Overall percentage and number of BE-negative urine samples across the trial will also be calculated. Subjects are likely to vary in their response to alternative reinforcers, especially between the three conditions, which will provide a range of scores that can be used to predict health outcomes. This variability should also permit exploratory analyses (see below) that will reveal threshold levels of change (e.g., 25%, 50%, 75% negative samples) that are associated with beneficial health outcomes.

Individual Counseling

To provide some benefit to all subjects in addition to health screening and monetary remuneration, all subjects will receive supportive behavioral therapy which provides clinical recommendations for reducing or ceasing COC use. Manual-guided treatment (the Substance Abuse and Mental Health Services Administration's Counselor's Treatment Manual: Matrix Intensive Outpatient Treatment for People with Stimulant Use Disorders) will be conducted weekly with a masters or graduate level psychologist, social worker or counselor, who will remain blind to assigned conditions. Based on our current experience, this counseling will also enhance retention.

Measures

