Other Analyses: This study will gather a rich data set of drug use indicators in addition to our primary indicator of weekly number of BE-negative urine samples. As such, analyses with other COC use indicators such as self-report from the TLFB and ASI, along with overall percentage of BE-negative urines and absolute number of BE-negative urines, will also be conducted to evaluate how COC use reductions indicated on those measures produce beneficial health outcomes. Inter-relationships between biomarker and physiological outcomes will be assessed using correlational analyses to determine how biomarker improvements predict physiological improvements from data collected at the same time point (e.g., cardiovascular biomarkers and ECG outcomes from Week 12), as well as from biomarker outcomes that precede physiological assessments (e.g., cardiovascular biomarkers from Week 6 and ECG outcomes from Week 12). Other planned exploratory analyses include comparison of our findings to any available normative data (e.g., lab normal ranges for ranges for CRP) to better demonstrate clinically meaningful improvements produced by COC use, as well as evaluation of reduction thresholds whereby subjects will be grouped based on percentage of BE-negative samples across the trial (i.e., 0-25%, 26-50%, 51-75% and 76-100% negative across the trial).

Sample Size Justification

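### The exploratory reduction tiers measure the level of in-trial cocaine use, not change from the subject's own baseline, so they mix true reduction with how much the subject used at entry

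*Combined protocol and SAP*

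**What the plan says.** All references are to the combined protocol and SAP.

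- **Section 7, Other Analyses** lists, among the exploratory analyses, an "evaluation of reduction thresholds whereby subjects will be grouped based on percentage of BE-negative samples across the trial". The bands are "0-25%, 26-50%, 51-75% and 76-100% negative across the trial".
- **Section 7, Defining Reduction in Frequency of COC Use** describes the same quantity as "threshold levels of change (e.g., 25%, 50%, 75% negative samples) that are associated with beneficial health outcomes", also as exploratory.
- **Section 4, Inclusion Criteria** requires "Self-report of recent cocaine use verified by a cocaine-positive urine sample" and "Meet moderate-severe Cocaine Use Disorder Criteria". Section 17 repeats that a subject "must present with a urine sample positive for cocaine/benzoylecgonine at the time of screening". None of these sets a minimum number of use days.
- **Section 7, Random Assignment** includes among the urn factors "COC use (>15/≤15 days used in the past 30"), taken from the Addiction Severity Index (ASI) at screening. The lower stratum has no stated floor.
- **Section 7, Table 1** schedules the TLFB and the ASI at baseline and at Weeks 4, 8 and 12.
- **Section 7, Other Analyses** also plans separate analyses of reductions shown on TLFB and ASI. It does not define them as change from baseline and does not link them to the tiers.

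**The concern.** An in-trial percentage of negative samples equals change only if all subjects start from the same use. Here they need not. The entry urine cannot serve as the reference, because every subject is positive at screening by rule and one sample does not measure frequency. A light user who changes nothing can therefore sit in a high reduction tier, while a heavy user who halves use sits in a low one.

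The effect on the result depends on how outcomes are compared across tiers, which the plan does not state. If outcome levels are compared, better health in the upper tiers may partly reflect subjects who were light users throughout. If improvement from baseline is compared, unchanged light users would dilute the upper tiers. Either way, a cut-point found this way could not be read as the amount of reduction needed.

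**Working it through.** **1. Denominator.** Three samples per week for 12 weeks is 3 × 12 = 36, as in Table 1. The maximum payments in Section 15 agree: 36 × $55 = $1,980 and 36 × $13 = $468. With 36 samples the four bands are 0-9, 10-18, 19-27 and 28-36 negatives (9/36 = 25%, 18/36 = 50%, 27/36 = 75%).

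**2. Assumptions.** The detection window is 72 hours, which Section 7 gives as an upper limit; 48 hours is the sensitivity case. I assume use on each day is independent with probability d/30, a sample is positive if any use falls in the preceding k days (k = 3 or 2), and no samples are missing.

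**3. Expected percent negative** is (1 − d/30)^k.

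| Use during trial | 72 h (k = 3) | 48 h (k = 2) |
|---|---|---|
| 4 days/30, unchanged | (26/30)³ = 65% | (26/30)² = 75% |
| 10 days/30, halved from 20 | (20/30)³ = 30% | (20/30)² = 44% |
| 15 days/30, halved from 30 | (15/30)³ = 12.5% | (15/30)² = 25% |

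**4. Tier placement**, simulated with 20,000 subjects per use level at 72 hours:

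| Use during trial | 0-25% | 26-50% | 51-75% | 76-100% |
|---|---|---|---|---|
| 4 days/30, unchanged | 0% | 7% | 81% | 11% |
| 10 days/30, halved from 20 | 36% | 63% | 1% | 0% |
| 15 days/30, halved from 30 | 98% | 2% | 0% | 0% |

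When an unchanged 4-day user is paired at random with a 20-to-10-day halver, the unchanged user is in the strictly higher tier in about 95% of pairs at 72 hours and 89% at 48 hours. The reverse occurs in under 0.1%.

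**5. Check without the independence assumption.** Take fixed weekly patterns, evening use (20:00), 08:00 samples and a 72-hour window. Someone who uses every Wednesday, Friday or Saturday and changes nothing has one positive sample a week, so 24/36 = 67% negative. Someone who uses every Tuesday or Sunday has two, so 12/36 = 33%. A daily user who cuts to Tuesday, Thursday and Saturday (7 to 3 days a week, 57% fewer) has 0/36 = 0% negative. The order is the same.

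**6. Can such light users enter?** In the same model, a 4-day user is positive on a random sample with probability 1 − (26/30)³ = 35% at 72 hours, or 1 − (26/30)² = 25% at 48 hours. They can enter, though less readily than heavy users.

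**7. Do the tiers mainly reflect entry use?** I assumed cohorts with entry use uniform over 2-30, 8-30 or 2-15 days, entry conditional on a positive screen, and several distributions of fractional reduction, some with a third to a half of subjects unchanged. Across both windows, tier correlated with true fractional reduction at about 0.63 to 0.83 (Spearman) and with entry use at about 0.31 to 0.54 in absolute size. Without the positive-screen condition, one cohort (2-30 days, 72 hours) gave 0.67 and 0.57.

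**The case against.** The strongest case against the point is as follows.

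- **The analysis is exploratory.** No aim, primary outcome or sample-size figure depends on it. Aims 1-3 use weekly negative counts in a mixed model, and Section 17 names endothelin-1 as primary. This stands and limits the severity.
- **TLFB and ASI analyses of reduction are already planned.** This stands in part. They could supply change from baseline, but the plan does not say so and does not tie them to the tiers.
- **Very light users are less likely entrants.** A 2-day user passes a random positive screen 1 − (28/30)³ = 19% of the time at 72 hours, against 1 − (10/30)³ = 96% for a 20-day user. Entrants must also be treatment-seeking with moderate-severe disorder. This makes misranking rarer but sets no frequency floor.
- **Urn randomization balances entry use.** It balances the three arms. The tiers are formed afterwards from in-trial results, so that balance does not carry over.

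Three stronger readings are tempting, and the documents support none of them. A reader might infer that the tiers sort subjects mainly by entry use, but the enrolled mix is not given and the assumed cohorts point the other way. A reader might infer that true reducers generally fall in the bottom tiers, but someone going from 20 to 4 days averages 65% negative and usually lands in the 51-75% band. Finally, a reader might take finding how much reduction is enough as a declared innovation of the trial, but the innovations listed in Section 1 mention no threshold.

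**Conclusion.** The point holds as a minor one. The tiers are labelled as reduction but measure level of use, and entry use contaminates them without dominating them in the cohorts examined. For the 4-day versus 20-to-10-day comparison, misranking is the usual result (about 95% of pairs at 72 hours, 89% at 48 hours). This rests on independent use days, a fixed detection window and complete samples; the fixed-pattern check gives the same order without independence. How often it would occur in the trial cannot be stated, because the documents do not give the distribution of entry use. The confirmatory analyses are untouched.

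**What to change.** In Section 7, Other Analyses, and the matching sentence under Defining Reduction in Frequency of COC Use:

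1. Keep the four BE-negative tiers, but label them level of in-trial use.
2. Compare health outcomes across the tiers with adjustment for baseline days of cocaine use (ASI or TLFB), or within the >15/≤15-day urn stratum. State whether outcome level or change from baseline is compared.
3. Add a companion analysis that groups subjects by change in TLFB use days from their own baseline to the intervention period.
4. Cross-tabulate the two groupings, so that readers see how many subjects in each urine tier had no TLFB reduction.

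The cost is analysis wording and a few tables, since the data are already collected. Three downsides should be stated. TLFB is self-reported, which is why the urine tiers stay. Percentage change is unstable at low baselines (2 to 1 day scores the same 50% as 20 to 10), so absolute change in days should be shown too. Selecting entrants on a positive urine invites regression to the mean, so some apparent reduction is expected without any real change.
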